Evaluation of MyoStrain™ in Clinical Practice

December 4, 2018

Investigators

[name] (PI), [name] (sub-investigator), [name] (study coordinator), [name] (study coordinator), [name], MS (study coordinator), [name] (study coordinator), [name], MS (study coordinator), [name] (study coordinator), [name] (MRI technologist), Department of Radiology, [name], (sub-investigator), Department of Cardiology

Purpose of Project

This study is designed to evaluate the use of MyoStrain cardiac MRI (CMR) pulse sequence to determine how the use of this single pulse sequence may alter treatment decisions and clinical outcomes in patients who are undergoing cardiac MRI. Strain Encoding (SENC) MRI technology is a rapid MRI scan providing detailed structural and functional imaging of the heart muscle, and is of great diagnostic value in guiding treatment decisions for patients with heart failure, drug toxicity (e.g. chemotherapy), and coronary artery disease. The goal is to determine if Myostrain CMR can detect subtle changes of heart damage earlier or with more sensitivity/specificity to ultimately improve patient outcomes and earlier intervention in their treatment course. The purpose is to determine if and how patients treatments are impacted (morbidity/mortality outcomes) as a result of using this SENC sequence, or if there is no significant difference between the current gold standard (regular cardiac MRI, ultrasound, or nuclear medicine heart scans).

Specific Objectives

- The primary objective is to evaluate the workflow for rapid MyoStrain testing in clinical practice, and its direct clinical impact in impacting clinical outcomes and changing therapeutic decision making by the treating physicians.
- The primary efficacy endpoint is the efficiency and accuracy of MyoStrain testing in obtaining global and segmental strain measurements including Global Circumferential Strain, Global Longitudinal Strain, Left Ventricular Ejection Fraction (LVEF), Mass, and Volumes. The workflow analysis will be performed by the investigators based on clinical experience compared to alternative imaging modalities.
- An additional primary efficacy endpoint will determine (quantitatively) the ability of Myostrain to influence treatment decisions by earlier detection of progressive heart disease when compared to the current gold standards.

Rationale/Background

Device Description

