- Myocardial Solutions, Inc. software measures tissue deformation or "strain" from the pulse sequence images. Quantitatively, "strain" is a mechanical property of deforming objects and measured as the percentile change in spacing between two points on a deforming object. For example, when muscle contracts, the muscle length is shortened. For example, a 30% shortening of the muscle is measured as strain of negative 30%.
- Measuring the shortening of the Heart Muscle results in two parameters that SENC quantifies: circumferential and longitudinal strain. Strain measurement depends on "direction" of measuring. For measuring the contraction of the heart muscle, there are two main directions that are typically used: 1) longitudinal strain, which describes the contraction of the myocardium that contributes to the base-to-apex contraction of the heart chambers; 2) circumferential strain, which describes the contraction of heart muscle fibers around the circumference of the chambers of the heart.

- Using SENC, circumferential and longitudinal strain values in 37 regions are measured in less than 2 minutes.

The Intended Use of the MyoStrain SENC MRI acquisition is:

- MyoStrain SENC software receives image data from MRI storage archives and performs viewing, image manipulation, communication, printing, and quantification of images. Available measurements include longitudinal and circumferential strain to quantitatively describe the wall motion of the heart. Tools are provided for display of regional motion properties of the heart.
- This unique sequence (SENC) will be used as an add-on to already-ordered cardiac MRI in many clinical scenarios (heart-failure, chemotherapy-related heart toxicity, inflammatory conditions such as sarcoid) to detect earlier progression or new heart-disease, that will change the management of patients (e.g. decreasing the amount of chemotherapy, changing chemotherapy regimen, or adding new cardiac failure drugs to prevent further decline or improve heart function).
- A report interface is provided. Measurement tools provide information that can be output in standardized or specialized report formats. This interface makes it possible to quickly and reliably fill out a complete clinical report of a cardiac imaging exam with strain. The results of the measurement tools are interpreted by the physician and can be communicated to referring physicians to support the determination of a diagnosis.

Clinical & Preclinical Testing

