- Stress testing for ischemia, performed on patients with suspected or known ischemic heart disease, demonstrated that measured strain was more sensitive in detecting stenosis in the coronary arteries compared to 1) conventional cine movies with qualitative assessment of abnormal wall motion under stress, and 2) the outcomes of revascularization of positively diagnosed patients. [5] [6] [7] [8] [9]
- Myocardial infarction studies show the value of strain measurements in assessing, with high accuracy, changes in regional function associated with damage from myocardial infarction. [10] [11] [12] [13] Quantification of changes in contraction is more accurate (more sensitive and specific) in associating with the depth of damage vis-à-vis subjective wall motion assessment.
- Cardiac mechanics studies illustrated other applications of SENC strain measurements in understanding the mechanics of the heart, especially the left and right ventricles. [14] [15] [16] [17] [18] These healthy subjects studies demonstrated, with high accuracy and precision, the ability to detect subtle variations in regional contraction. Also, quantification revealed variations in contractility as a result of diseases affecting the right ventricle, which is very hard to assess using echocardiography because of the position of the right ventricle close to the ribs and the sternum and its geometry.

Methodology

This prospective study will include up to 100 patients who will be enrolled based on meeting the stated inclusion/exclusion criteria. Upon completion of the informed consent, patients will undergo SENC MyoStrain testing in a Siemens Manufacturer Scanner with a validated pulse sequence. The testing will incorporate baseline MyoStrain Testing in which 3 short axis slices and 3 long axis slices will be planned for imaging and then recorded with MyoStrain testing.

System setup and testing methodology will follow the Myocardial Solutions SENC User's Manual 4.x. The SENC MyoStrain Test procedure is a quick and simple analysis which will require only one series of images. The importation of the images from the scanner and organization of these images is mostly automated and requires very minimal interaction to function correctly. The workflow of the SENC MyoStrain test requires only one scan and analysis phase allowing the complete scan to be completed within 2 minutes after imaging planning.

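### The additional primary endpoint credits treatment changes to earlier detection of progressive disease, but the trial as described can show only that decisions change

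*Protocol*

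**What the plan says.** Under Specific Objectives, the additional primary efficacy endpoint is to determine quantitatively "the ability of Myostrain to influence treatment decisions by earlier detection of progressive heart disease when compared to the current gold standards". Purpose of Project names the benchmark when it asks whether SENC makes a difference, "or if there is no significant difference between the current gold standard (regular cardiac MRI, ultrasound, or nuclear medicine heart scans"). The same paragraph states a wider aim: "The goal is to determine if Myostrain CMR can detect subtle changes of heart damage earlier or with more sensitivity/specificity". It also mentions morbidity and mortality, and the primary objective mentions clinical outcomes.

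On conduct, the intended-use text under Rationale/Background says: "This unique sequence (SENC) will be used as an add-on to already-ordered cardiac MRI in many clinical scenarios". Results go to the physician and "can be communicated to referring physicians to support the determination of a diagnosis". Methodology says: "This prospective study will include up to 100 patients", and "The testing will incorporate baseline MyoStrain Testing in which 3 short axis slices and 3 long axis slices will be planned for imaging". Methodology and Data Management then cover PACS storage of the clinical and research scans and transfers to the manufacturer: the first 20 sets of raw images and outcome reports, and up to five scans per quarter, for quality control, certification and technologist proficiency.

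Neither section describes a repeat scan, a follow-up time, a way of collecting outcomes, a confirmatory reference, or a treatment plan written before the SENC result is known.

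**The concern.** The endpoint joins three claims: that a treatment decision changed, that it changed because SENC found disease, and that the disease was progressive and found sooner than the standard would have found it. The first can be counted, provided the decision without SENC is known. The other two need information from outside the two tests.

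The critical patient is abnormal on SENC and normal on the standard. That patient has either early disease or a false-positive SENC result. If the standard really is the gold standard, the SENC-only finding is a false positive by definition, and earlier detection cannot be shown against it. If it is not, something else must arbitrate, and nothing is named.

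What is at stake is the conclusion on a primary endpoint. The intended-use text expects SENC findings to alter chemotherapy or add cardiac drugs. Without arbitration, a change prompted by a false positive looks the same in the data as one prompted by true early disease.

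**Working it through.** The protocol gives no error rate, power, effect size, event rate or follow-up time, so there is no figure to reproduce. The check sets what the endpoint needs against what is described, then illustrates the gap.

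**What each part of the endpoint needs**

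- *Changed decision*: a plan without SENC and a plan with it. Decisions rest with the treating physicians and SENC results can reach them, but no plan recorded beforehand is described.
- *Detection*: a reference independent of both methods. None is described for these patients. The comparisons under Clinical & Preclinical Testing (tagged MRI, speckle tracking, delayed enhancement, coronary stenosis) come from other studies and do not classify a discordant result here.
- *Earlier*: a later diagnosis that the SENC finding precedes. SENC is added to the ordered MRI, and no later assessment is described.
- *Progressive*: at least two measurements over time. Only baseline testing is described.

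**Illustration 1: the same count fits opposite truths.** All inputs are assumed. Let m = 60 patients be normal on the standard, of whom 12 are abnormal on SENC. With p the prevalence of true early disease among the 60:

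SENC-only positives = m·p·Se + m·(1 − p)·(1 − Sp)

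| p | Se | Sp | True positives | False positives | Total | Share true |
|---|---|---|---|---|---|---|
| 0 | 0.80 | 0.80 | 0 | 60 × 0.20 = 12 | 12 | 0% |
| 0.10 | 0.80 | 0.867 | 60 × 0.10 × 0.80 = 4.8 | 54 × 0.133 = 7.2 | 12 | 40% |
| 0.20 | 0.80 | 0.95 | 60 × 0.20 × 0.80 = 9.6 | 48 × 0.05 = 2.4 | 12 | 80% |
| 0.20 | 1.00 | 1.00 | 60 × 0.20 = 12 | 0 | 12 | 100% |

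Baseline data alone cannot tell these rows apart. The assumed ranges were 40 to 80 of 100 patients normal on the standard, p from 5% to 20%, and Se/Sp of 0.90/0.95, 0.80/0.90 or 0.80/0.80. Over these the expected SENC-only count runs from 1.8 + 1.9 = 3.7 to 12.8 + 12.8 = 25.6. The share that is true disease runs from 0.04/(0.04 + 0.19) = 17% to 0.18/(0.18 + 0.04) = 82%.

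**Illustration 2: one data set, two readings.** Only n = 100 comes from the protocol, where it is a maximum. Assume 24 positive on both methods, 0 on the standard only, 10 on SENC only and 66 negative on both, with all concordant results correct.

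- All 10 diseased: standard sensitivity 24/34 = 70.6%, SENC 100%.
- None diseased: SENC specificity 66/76 = 86.8%, standard 100%.

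**Illustration 3: the treatment endpoint.** If 6 of those 10 patients have treatment changed, the change proportion is 6/100 = 6%, with exact (Clopper-Pearson) 95% CI 2.2% to 12.6%. The number of those changes that rest on true disease can be anything from 0 to 6.

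**The case against.** The best counter-argument is that silence is being read as design. Methodology does not limit a patient to one scan, and the word baseline can suggest later ones. The sentence "The workflow of the SENC MyoStrain test requires only one scan and analysis phase" describes how a single test is run, not how many time points the study has, so it is no evidence of a single-time-point design. Morbidity and mortality are named, and the patients are already in clinical work-up. All of this stands. A reader might infer that the trial will have no follow-up or outcome data at all; the protocol supports only that none is described.

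A reader might also infer that every change prompted by a false positive will be scored as earlier detection. The protocol states no scoring rule, and one could be set in an SAP that is not shown. But an SAP cannot create a later assessment, an independent reference or a plan recorded before SENC. If those are not collected, no scoring rule can fill the gap.

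A third inference would be that the illustrations say something about SENC's accuracy. They do not. Having no standard-only positives and all concordant results correct produces the sharp contrast, and the binary call is imposed on continuous strain measurements. The sensitivity/specificity aim is in any case a stated goal, not an endpoint. Positivity rules and cross-tabulations are SAP matters and would not resolve discordant results.

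**Conclusion.** The point holds in a limited form. As described, the trial can measure whether treatment decisions change, if the prior plan is recorded. It cannot show that a change reflects disease found earlier, or progressive disease, rather than a SENC false positive. This rests on setting the endpoint's wording beside Methodology, Data Management and the add-on use, not on any calculation.

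Its size cannot be derived from the documents. The illustrations show only that, without a reference or later information, the share of SENC-only findings that is true disease is not identifiable: 0% to 100% for one and the same count. The documents do not support the stronger statements that outcomes will certainly go uncollected or that SENC is inaccurate. The point should be fixed because it concerns the conclusion of a primary endpoint and the remedy is cheap.

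**What to change.** Restate the endpoint as the proportion of patients, with exact confidence interval, whose treatment decision changes after the SENC result. Compare the treating physician's plan recorded on the standard report with the plan recorded after SENC is released. Remove the attribution to earlier detection and to progression from the endpoint and from its conclusion.

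Use the word earlier only if later diagnosis or imaging is abstracted from records at one horizon stated in the protocol, for all patients, including those negative on both methods. Label that part descriptive: SENC-positive patients may be re-imaged more often, and treatment started because of SENC may alter what is found later.

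No scan or visit is added. The costs are a short form and a rule that the standard report and the first plan come before SENC release. That rule is a small change to reporting flow, and since workflow is itself part of the primary objective, it should be noted in the workflow evaluation. The optional abstraction adds one record review per patient. The main price is a weaker claim: influence on decisions, not proof of earlier detection.

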The MyoStrain SENC CMR Imaging System is limited to observational evaluation within the United States. The MyoStrain system has European approval with an EC Certificate according to Directive 93/42/EEC on Medical Devices, Annex II excluding Section 4 (CE 657862) in respect of: Design, development and manufacture of software for the quantification of cardiac MRI images.

Strain Encoding (SENC) MRI technology is a fast MRI scanning diagnostic test that measures the contraction of the heart muscle in one to three heartbeat(s) per image plane, depending on the specific pulse sequence and associated MRI Manufacturer Scanner type and software version. This means that patients can be scanned very fast, in many cases while breathing, and a complete view of the ventricles' health can be obtained in less than a minute. Quantitative assessment of the strength of the heart muscle can have many clinical applications, but its highest value is in the two largest heart disease populations: those patients with heart failure and coronary artery disease.

SENC is an MRI Pulse Sequence for Strain Encoding

- A pulse sequence is an algorithm that instructs the MRI scanner to acquire certain types of images. Any MRI scanner has a large number of pulse sequences for general and specialized imaging of different parts of the body. They produce images that show different anatomies, physiologies, or pathologies of the different tissues of the body. For imaging the heart, there is a group of specialized pulse sequences that can show different aspects of the heart, including, but not limited to, the structure of the heart, the motion of the heart, the tissue characterization of the muscle, the flow of the blood, the structure of the vessels, and more.
- The Strain Encoding (SENC) pulse sequence is a specialized pulse sequence that produces images of the heart muscle that reveal the underlying contraction of the muscle of a healthy heart and associated weaknesses in case of disease. The measurements of the deformations of regions within the heart muscle ("myocardium") associated by contraction and relaxation during a single heartbeat is measured by the mechanical quantity called "strain."

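### The additional primary endpoint on treatment decisions has no described record of the physician's plan on the standard MRI before SENC is seen, so SENC's influence cannot be separated from that of the standard MRI

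*Protocol*

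**What the plan says.** Specific Objectives in the protocol names an additional primary efficacy endpoint, to be determined quantitatively: the "ability of Myostrain to influence treatment decisions by earlier detection of progressive heart disease when compared to the current gold standards". The primary objective has two parts. One is to "evaluate the workflow for rapid MyoStrain testing in clinical practice"; the other is the effect on clinical outcomes and on the treating physicians' therapeutic decisions. Purpose of Project spells out the comparator as the "current gold standard (regular cardiac MRI, ultrasound, or nuclear medicine heart scans".

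On delivery, the intended-use section states: "This unique sequence (SENC) will be used as an add-on to already-ordered cardiac MRI in many clinical scenarios". Inclusion Criteria restricts entry to patients already scheduled for cardiac MRI. Methodology states that "This prospective study will include up to 100 patients" and gives all of them SENC after consent.

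On reporting, the intended-use section says that the software interface can "quickly and reliably fill out a complete clinical report of a cardiac imaging exam with strain" and that results "can be communicated to referring physicians to support the determination of a diagnosis".

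Methodology otherwise covers slice planning, scanning and software workflow. Data Management covers image storage and the transfer of scans for quality control. The one comparison method described is the investigators' own experience with other modalities, and it applies to the workflow analysis.

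**The concern.** Influence on a treatment decision is a comparison between what the physician decides with SENC and what the same physician would have decided without it. All enrolled patients also have a standard cardiac MRI, which was ordered for clinical reasons and may itself change treatment. If only the decision taken after both results is known, a change prompted by the standard MRI looks the same as one prompted by SENC.

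What is at stake is one of the two stated primary efficacy endpoints and the decision-making part of the primary objective. The endpoint on efficiency and accuracy of the strain measurements is not affected.

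**Working it through.** The protocol gives no rate, margin, error level or power for this endpoint, and the figure of 100 patients is a ceiling without a derivation. There is no stated number to reproduce. The check has three parts.

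**1. What the endpoint needs against what is described**

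| Needed to attribute a decision to SENC | Described in the protocol |
|---|---|
| Plan based on the standard MRI alone | No |
| Order in which standard and SENC results are disclosed | No |
| Withheld or randomised disclosure, control group, or panel deciding with and without SENC | No |
| Both tests in each patient | Yes (intended-use section, Methodology, Inclusion Criteria) |
| Stored images from the clinical and research scan | Yes (Methodology, Data Management) |

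The last two rows allow a within-patient comparison of images. Re-reading the stored scans could show disease visible only on SENC. It would not show what the treating physician would have done without that finding.

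**2. Why more patients do not help**

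Assume 100 patients, and grant that a plan from before any imaging is known. Suppose that 30 plans have changed once both results are in (an assumed count). Each of these cases produces exactly that observation:

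- Standard MRI alone would have changed the same 30 plans in the same way. SENC altered 0 of 100 plans.
- Standard MRI alone would have changed none. SENC altered 30 of 100.
- Standard MRI alone would have changed all 100, and SENC returned 70 to the starting plan (100 − 70 = 30 still changed). SENC altered at least 70 of 100.

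With 50 patients and 15 changes the same cases give 0, 15 and at least 35 of 50, which are again 0%, 30% and at least 70%. The ambiguity is one of identification, and it does not shrink with n.

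**3. What a two-step record would give**

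Let x be the number of patients whose plan differs between the record before SENC and the record after it, out of n. The exact (Clopper-Pearson) 95% limits are:

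- lower = 2.5% quantile of Beta(x, n − x + 1)
- upper = 97.5% quantile of Beta(x + 1, n − x)

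The counts below are assumed. The smaller n is shown because 100 is a maximum.

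| x/n | Estimate | Lower | Upper |
|---|---|---|---|
| 10/100 | 10% | Beta(10, 91): 4.9% | Beta(11, 90): 17.6% |
| 5/50 | 10% | Beta(5, 46): 3.3% | Beta(6, 45): 21.8% |

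These intervals cover sampling error only. They do not cover bias from a hedged first plan, or patients whose first plan was not recorded in time.

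**The case against.** **The point rests on silence.** Case report forms are not shown, and one of them could hold a decision record. This stands in part: the document supports only that no record is described, not that none is collected. It does not remove the point, because when a result is disclosed and what the physician records first are study procedures. Methodology lists the procedures without them. Nor is this something an analysis plan could supply later.

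**Each patient is his or her own control.** That is true for the images, and for this reason no separate control group is needed. It is not true for decisions.

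**Stored scans linked to later treatment would carry some information.** They would, but they would not supply the decision without SENC.

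Two stronger readings are tempting and should not be adopted.

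- A reader might infer from the intended-use section that both results reach the physician in one report. Those lines state what the software makes possible, not what the study does. Joint release is possible but not established.
- A reader might infer that, if a fraction of patients change plan after both results, SENC's effect lies between zero and that fraction. That holds only for SENC's share of the changes observed. It ignores changes that SENC cancels, as the third case in the working shows, so it does not bound the proportion of plans that SENC alters.

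**Conclusion.** The concern holds in a limited form. A primary endpoint asks for a quantitative comparison of decisions with and without SENC, and the protocol describes no procedure that would yield the decision without it. As described, the effect on decisions is not identified at any number of patients.

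The direction and size of any error are unknown, because the protocol gives no rate of treatment change and the counts used above are assumptions. The conclusion assumes that the study is run as Methodology describes and that no decision form exists elsewhere; if one does, citing it in the protocol would largely settle the point.

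This should be fixed before patients are scanned, because a plan that was not recorded beforehand cannot be reconstructed.

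**What to change.** In Methodology, add a two-step decision record:

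1. The standard cardiac MRI report is issued as usual, without delay and without strain values. The treating physician records the intended plan from it before seeing the SENC result.
2. The physician records the plan again after seeing the SENC result.

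SENC results stay available at any time. Patients whose SENC result was seen before the first plan was recorded are logged and reported separately.

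In Specific Objectives:

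- Define the endpoint as the proportion of patients whose plan differs between the two records, in either direction, with an exact 95% interval.
- For each difference, note whether it followed from a finding on SENC that was absent on the standard MRI. Report this as SENC-only detection and not as confirmed earlier detection, since no follow-up is described.
- State that the endpoint measures added influence over standard cardiac MRI only, not over ultrasound or nuclear scans.
- Keep the interval between the two records out of the workflow timing.

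**Cost.** Two short forms per patient, from physicians who may be outside the study team and need reminding, and a reading order in which the standard report is completed first. No extra scans, visits or patients.

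**Limits.** The first plan is an intention. A physician who expects a second result may hedge it, which may bias the endpoint in favour of MyoStrain and should be stated as a limitation. The record prescribes no treatment, but Device Description says that the system is "limited to observational evaluation within the United States", so the sponsor should confirm that the record fits that restriction.

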Data obtained for the clinical and research scan will be stored in PACS. KUMC will provide the first 20 de-identified MyoStrain raw images and outcome reports to MyoCardial Solutions.

Inclusion Criteria

- Patients already scheduled for diagnostic testing with commercially available imaging modality (cardiac MRI)
- The patient population will include (but not limited to), those being evaluated for heart disease and heart failure that may be related to vascular disease (coronary artery disease), drug related heart failure (chemotherapy, alcohol), inflammatory systemic conditions (sarcoidosis, amyloidosis, lupus), myocarditis, and/or infectious etiologies
- Provided written informed consent

Exclusion Criteria

- Contraindication to Magnetic Resonance Imaging

Risks

The SENC MyoStrain software with the associated MRI Manufacturer Scanner pulse sequence is a noninvasive imaging technology. There is minimal direct physical risk for imaged subjects as it is an MRI procedure that does not require any invasive intervention or injections. As such the risks are limited to those typical for conventional non-contrast (e.g. without contrast injection) MRI exams. Subjects will be evaluated as an inclusion criteria for potential contraindications to MRI imaging. Considering image acquisition is very fast (< 5 min) reducing time within the magnetic bore, risks of claustrophobia or anxiety may be reduced compared to traditional MRI tests.

The MSI SENC MyoStrain software has been tested and validated following ISO 14971 (Medical Devices – Application of Risk Management to Medical Devices).

Detailed risk assessments have been done by Myocardial Solutions, Inc. throughout the software development. The company routinely performs management review that include analysis of device performance, change control (design, process, labeling), and corrective and preventative action for the product.

Myocardial Solutions' risk assessment has been completed and clinical risks have been reduced as far as possible by device design, labeling, and training protocols for intended users. There are no unacceptable residual clinical risks based on the risk/benefit reviews.

Data Management

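### The comparison behind the treatment-decision primary endpoint is unresolved, and treatment under SENC in place of a gold standard cannot be observed in this add-on design

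*Protocol*

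**What the plan says.** The third bullet of Specific Objectives (Protocol) adds a primary efficacy endpoint, to be determined quantitatively: the ability of MyoStrain to "influence treatment decisions by earlier detection of progressive heart disease when compared to the current gold standards".

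The Purpose of Project speaks of the comparison in two ways. Its opening sentence asks how the single sequence "may alter treatment decisions and clinical outcomes in patients who are undergoing cardiac MRI". Its last sentence asks whether patients' treatments and outcomes are affected, "or if there is no significant difference between the current gold standard (regular cardiac MRI, ultrasound, or nuclear medicine heart scans". Between the two, it speaks of detecting damage earlier or with greater sensitivity or specificity.

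The design is described elsewhere:

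- Intended Use of the MyoStrain SENC MRI acquisition: SENC "will be used as an add-on to already-ordered cardiac MRI in many clinical scenarios".
- Inclusion Criteria: "Patients already scheduled for diagnostic testing with commercially available imaging modality (cardiac MRI".
- Methodology: up to 100 consenting patients, all of whom undergo SENC. No other group is described.

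**The concern.** A primary endpoint needs one comparison. The third objective can be read in two ways:

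- **Incremental:** cardiac MRI plus SENC against cardiac MRI alone.
- **Head-to-head:** SENC against a gold standard.

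The Purpose contains wording for each and does not choose between them.

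The choice affects what the trial may conclude. If a positive finding on either scan counts as detection, the incremental result cannot fall below zero. The head-to-head result can, because it subtracts the patients whom MRI finds and SENC misses. An incremental rate presented under the words of the third objective could be taken as evidence that SENC does better than cardiac MRI when the data show no such thing.

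Part of the stated comparison is also out of reach. No treating physician is without the cardiac MRI, and two of the three named gold standards are not required by the protocol.

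**Working it through.** **Step 1. What each patient contributes.** By the Inclusion Criteria and the Intended Use text, every participant has the clinical cardiac MRI. By the Methodology, every participant also has SENC. No ultrasound or nuclear scan is required. The protocol describes no management plan recorded before SENC is seen and no separate reading of the two scans.

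| Quantity | Obtainable from the protocol as written? |
|---|---|
| Actual treatment or outcome under SENC in place of cardiac MRI | No; MRI is always present |
| The same against ultrasound or nuclear scans | No; MRI is always present, and these scans are not required |
| Paired detection, SENC against MRI | Only if the two are read separately; not described |
| Change in plan from MRI alone to MRI plus SENC | Only if the MRI-alone plan is recorded first; not described |

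**Step 2. How far the two readings can part.** The protocol gives a ceiling of 100 patients with no rates, effect size or margin behind it, so there is no figure of its own to reproduce. The counts below are assumptions for illustration. They count detections, as a stand-in for the treatment decisions that detections would prompt.

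Let n = 100, b = patients detected by SENC only, and c = patients detected by cardiac MRI only. A positive finding on either scan counts as detection in the incremental reading; this too is an assumption.

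- Incremental gain = b/n, with Wilson 95% CI.
- Head-to-head difference = (b - c)/n, with paired Wald 95% CI using SE = sqrt[((b + c)/n - ((b - c)/n)²)/n], and exact McNemar p.
- Gap = b/n - (b - c)/n = c/n.

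For b = 15, c = 10: the gain is 15/100 = 15%. The difference is 5/100 = +5 points, with SE = sqrt[(0.25 - 0.0025)/100] = 0.0497. Then 1.96 × 0.0497 = 0.0975, so the interval is -4.8 to 14.8 points.

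| b | c | Incremental (95% CI) | Head-to-head, points (95% CI) | McNemar p |
|---|---|---|---|---|
| 15 | 0 | 15% (9.3 to 23.3) | +15 (8.0 to 22.0) | 0.0001 |
| 15 | 5 | 15% (9.3 to 23.3) | +10 (1.5 to 18.5) | 0.041 |
| 15 | 10 | 15% (9.3 to 23.3) | +5 (-4.8 to 14.8) | 0.42 |
| 15 | 15 | 15% (9.3 to 23.3) | 0 (-10.7 to 10.7) | 1.0 |
| 10 | 15 | 10% (5.5 to 17.4) | -5 (-14.8 to 4.8) | 0.42 |
| 20 | 10 | 20% (13.3 to 28.9) | +10 (-0.6 to 20.6) | 0.099 |

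**Step 3. Reading the table.** The point estimates agree when c = 0; the limits in that row differ only because the interval methods differ. At c = 5 with b = 15, both readings are positive. As c grows the head-to-head result loses support while the incremental result does not move. The sign of the estimate reverses only where SENC detects fewer patients than MRI.

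**The case against.** The strongest reply is that the protocol is consistent if read generously. The opening Purpose sentence poses the incremental question. Regular cardiac MRI can mean cardiac MRI without the SENC sequence, and the closing words of the Purpose can be taken as the matching null. On that reading the Purpose, the Intended Use text and the Inclusion Criteria all describe MRI with SENC against MRI alone.

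Much of this stands. A reader might infer that the protocol defines a replacement contrast in one place and an add-on contrast in another. It does not: the objectives never say that SENC replaces anything, and the Intended Use text describes how the sequence is used without defining an endpoint. The ambiguity already lies within the Purpose and the third objective. The generous reading fails, however, to account for ultrasound and nuclear scans as comparators, or for the language of sensitivity and specificity.

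It can also be said that the counts are invented, that they concern detections while the endpoint concerns decisions, and that the protocol states no either-positive rule. All true. The counts show only that the choice of comparison can matter. Nor does the protocol say that an incremental rate will be presented as superiority over MRI; that is a risk left open by the wording.

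Finally, a statistical analysis plan may exist. It could choose between the readings, but it could not supply treatment decisions made on SENC alone.

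**Conclusion.** The point holds as an unresolved and partly undeliverable comparison. The third objective and the last Purpose sentence claim more than a single group with cardiac MRI plus SENC can show. The two readings differ by c/n, the MRI-only share. With assumed counts of 15 and 10 in 100 that is 10 points: 15% against +5 points, whose interval includes zero. The size rests on assumed counts and the either-positive rule.

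Three stronger conclusions are tempting and are not supported:

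- That the readings must give different results. They can, but they coincide when no patient is detected by MRI only.
- That no SENC-versus-MRI comparison is possible. Only actual treatment and outcomes under SENC alone are unobservable. Detection or intended management could be compared within patients if the scans were read separately and the intended decision recorded.
- That the design already supports the incremental reading and only the words need changing. Without a plan recorded on MRI alone before SENC is seen, the incremental effect is not identified either.

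**What to change.** Amend the third objective and the last sentence of the Purpose to state one comparison: the change in the treating physician's recorded management plan from the already-ordered cardiac MRI alone to cardiac MRI plus SENC.

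With that:

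1. Add to the Methodology that the plan on cardiac MRI alone is recorded before the SENC result is revealed, and recorded again afterwards.
2. Remove ultrasound and nuclear scans as comparators for this endpoint.
3. State that no claim will be made about the treatment influence of SENC in place of a gold standard.
4. Make any SENC-versus-MRI comparison of detection secondary and paired, showing both the SENC-only and the MRI-only cells, and do it only if the two are read separately.

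No additional patients or scans are needed. The cost is an amendment, one extra recorded item per patient (the plan before SENC) and, if the optional detection comparison is kept, the effort of separate readings. The sponsor gives up a gold-standard claim on treatment decisions that the design could not support.
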